1.1 OBJECTIVE

This study's goals are to: 1) use free-breathing magnetic resonance imaging (FB-MRI) to measure fetal body composition in the third trimester and 2) determine how the FB-MRI quantitative measurements compare to growth parameters at birth.

1.2 HYPOTHESES AND SPECIFIC AIMS

To accomplish our objectives, our aims and hypotheses are as follows:

Specific Aim 1:

In a prospective study in women with healthy pregnancies and women with fetuses that have intrauterine growth restriction (IUGR) and gestational diabetes, we will quantify fetal subcutaneous, visceral, and brown adipose tissue volumes and proton-density fat fraction (PDFF) using FB-MRI in the third trimester.

Hypothesis 1: Using a FB-MRI technique we will find the following,

- 1) The growth restricted fetus will have less visceral, subcutaneous, and brown adipose tissue volume and PDFF when compared to healthy fetuses and fetuses whose mothers have gestational diabetes.
- 2) Fetuses whose mothers have gestational diabetes will have a greater subcutaneous and visceral adipose tissue volume and PDFF compared to healthy fetuses.

Specific Aim 2:

In a prospective study in pregnant women and their fetuses, we will compare volume and PDFF measurements of fetal visceral, subcutaneous, and brown adipose tissue obtained with FB-MRI to birth growth parameters of these infants.

Hypothesis 2: The volume and PDFF of fetal visceral and subcutaneous adipose tissue will correlate positively with birth weight and length z-score.

1.3a. BACKGROUND:

Pediatric obesity is a public health crisis with increasing prevalence worldwide. 19% of children and adolescents in the United States are obese¹. Pediatric obesity is associated with an increased risk for adult onset metabolic syndrome, which refers to the co-occurrence of obesity, insulin resistance, dyslipidemia, hypertension, and non-alcoholic fatty liver disease². There is also a tremendous amount of evidence suggesting that obesity and the metabolic syndrome have fetal origins due to abnormal fetal growth and maternal conditions³⁻⁶.

Impaired fetal growth is a major cause of perinatal morbidity and mortality. Infants with intrauterine growth restriction (IUGR) and infants who are born small for gestational age (SGA) and large for gestational age (LGA) have an increased risk for future obesity, insulin resistance, cardiovascular disease, and associated metabolic complications. IUGR infants have been found to have insulin resistance due to epigenetic changes in the liver and reduced pancreatic beta cell mass³. IUGR infants also exhibit satiety dysregulation secondary to impaired leptin and ghrelin⁴.

Maternal conditions such as obesity and hyperglycemia in pregnancy may also play a role in the infant's risk factors for obesity. Meta-analyses demonstrated that a maternal body mass index (BMI) in the obese range, glycemia, and birthweight are related to childhood obesity and insulin resistance^{5,6}. In short, a person's fetal experience and birth weight appear to be surrogates for future metabolic health.

Body composition parameters can also be important biomarkers for future metabolic health. Body composition is the measurement of the different tissues of the body including adipose tissue muscle, and bone. Fat can be categorized by location (visceral vs. subcutaneous) and type (white vs. beige vs. brown). Visceral fat is located beneath the abdominal muscles while subcutaneous fat sits directly beneath the skin. Visceral fat is composed of mainly white fat and is metabolically active. Visceral fat releases free fatty acids into the circulation which can lead to insulin resistance⁷, dyslipidemia⁷, hypertension^{8,9}, and fatty liver^{8,9}. Studies demonstrated a significant correlation between the proportion of visceral adiposity in children and adults with obesity and the metabolic syndrome⁷. In infants, increased fat mass gains and rapid weight gain (weight z-score >0.67 in the first two years of life) have been associated with later onset obesity, insulin resistance, hypertension, and non-alcoholic fatty liver disease^{8,9}.

In contrast to white adipose tissue, brown adipose tissue is responsible for thermogenesis and energy expenditure, and is generally located near the spine, and supraclavicular, axillary, and supraclavicular regions. Traditionally, brown adipose tissue was thought to be only present in the newborn. However, research now demonstrates that brown adipose tissue is present in children and adults¹⁰. When compared to white adipose tissue, brown adipose tissue has a higher water:adipose tissue ratio, is mitochondria-rich, and has a dense supply of capillaries for oxygen consumption. Research demonstrates that brown adipocytes may protect against insulin resistance and obesity. There is now research being conducted on how to convert visceral white adipose tissue to brown adipose tissue¹¹.

It is important to be mindful that body composition can be measured using different technologies: dual-energy X-ray absorptiometry (DXA), computed tomography (CT), ultrasound, air displacement plethysmography (ADP, commercially known as the PeaPod), and magnetic resonance imaging (MRI). DXA and ADP cannot be used in a fetal model due to poor image quality. DXA is able to estimate the amount of subcutaneous and visceral adipose tissue within the android region, and correlates well with

CT¹². However, DXA and CT both require radiation, which is undesirable for the fetus and child. While ultrasound does not involve radiation, is an inexpensive imaging tool, and can be used in the utero and extra-utero environment, ultrasound is dependent on the skill of the sonographer and results can be variable. In contrast, MRI is a noninvasive imaging tool that does not involve ionizing radiation and can be used to accurately and longitudinally quantify the volume of adipose tissue. MRI can also measure the proton-density fat fraction (PDFF) in percent, which is used as a biomarker for tissue fat content.

Fetal MRI is becoming increasingly utilized as an adjunct to ultrasound for maternal or fetal conditions related to pregnancy. The American College of Obstetricians and Gynecologists released a statement in 2017 stating that MRI is not dangerous and should be used prudently to answer a clinical question. Today, MRI is commonly utilized in cases of placenta accreta¹³ and fetal anomalies such as congenital diaphragmatic hernia, congenital heart disease, and neurological anomalies. There are difficulties with fetal MRI due to lack of control of fetal movement. Our group has developed a free-breathing (FB) MRI technique and has utilized this technology in adults, pregnant women, adolescents, and infants¹⁴⁻¹⁸.

To date, there has been little research pertaining to fetal body composition using MRI. Previously, using T1-weighted MR images, it has been difficult to detect adipose tissue in the second trimester^{19,20}. Blondiaux et al (2018) looked at subcutaneous adipose tissue in T1-weighted images starting in the second trimester and found the signal was isointense at 26 weeks and all areas were hyperintense by 33 weeks in a progressive fashion from the nuchal region, buttocks, thigh and back²¹. However, now using 3T MRI for fetal imaging, subcutaneous adipose tissue is more easily identified in the mid and late second trimester²².

1.3b. PRELIMINARY DATA:

[figure not shown]

Figure 1. Radial free-breathing MRI was performed on infants. Visceral (VAT), subcutaneous (SAT) and brown adipose tissue (BAT) was measured on the PDFF maps.

Our research group's goal is to use FB-MRI to better understand the early origins of obesity so that we can develop strategies to prevent and treat this disease. In adolescents, we have performed FB-MRI scans to quantify hepatic fat and compared these results to reference breath-held (BH) MRI scans¹⁶. BH-MRI exhibited artifacts and on average covered only 74% of the liver¹⁶. In contrast, FB-MRI demonstrated significantly higher image quality and covered 100% of the liver¹⁶. Moreover, when image artifacts in BH-MRI were avoided, hepatic PDFF from FB-MRI significantly correlated with BH-MRI with a concordance correlation coefficient of >0.99¹⁶. In infants, we have used FB-MRI to quantify subcutaneous adipose tissue, visceral adipose tissue, brown adipose tissue, and hepatic fat (Figure 1)¹⁸. Of note, elevated hepatic PDFF was measured in an infant born large for gestational age to a mother with insulin resistance and was noted to be greater compared to control infants¹⁸. In summary, these data show that FB-MRI can measure body composition and suggest that the capabilities of FB-MRI can be extended to the fetus.

1.4 JUSTIFICATION FOR THE STUDY:

Significance and Innovation

Pediatric obesity is a significant public health problem in the United States. Pediatric obesity is easy to diagnose, but difficult to treat. If there were early predictors in utero of risk for developing obesity, then early intervention programs could be applied and close nutritional monitoring by the general

pediatrician could be performed. To solve this problem, we propose a novel imaging technology, FB-MRI, to quantify body composition. Based on our preliminary evidence, we believe FB-MRI will allow:

- Early prediction of preliminary growth
- Close nutritional monitoring given known amount of adipose tissue

While we know this is an expensive tool that cannot be practically used in the clinical setting, this can be a tool to help further research on pediatric obesity. This may also lead to development of further cost effective tools for the clinical setting.

Investigators

2.1 STUDY DESIGN

This is a prospective pilot study that will be used to generate data to provide a power analysis for a larger, longitudinal study that will follow fetuses at risk for obesity.

2.2 PRIMARY OUTCOMES:

The primary outcome will be visceral adipose tissue volume and PDFF for the three patient populations: mothers with growth restricted fetuses, mothers with gestational diabetes, and mothers with healthy pregnancies.

2.3 SECONDARY OUTCOMES:

The secondary outcomes will be subcutaneous and brown adipose tissue volume and PDFF, as well as hepatic PDFF, for the three patient populations listed above. Another secondary outcome will be growth parameters of the neonates.

2.4 POTENTIAL RISKS AND BENEFITS:

Subjects may receive no benefit from participating in this study. However, information from this study may improve the understanding of childhood obesity, inform management strategies, and may help prognosticate which infants are at higher risk for obesity.

The research MRI scans required for this study do not require sedation, involve ionizing radiation, or require any contrast administration. MRI scans are a painless test. In other words, the FB-MRI performed for research purposes will NOT require contrast or sedation. However, patients/subjects can experience claustrophobia inside the MRI scanner. Patients with a history of claustrophobia will be excluded from this study. Noise from the scanner during an MRI scan will be mitigated by providing earplugs and headsets to the patients/subjects. Lastly, because MRI scans use magnetic fields, subjects with any metal (e.g., internal metal clips or implants) will be excluded from the study. All subjects will be asked to remove any metal (i.e. earrings, metal belts, etc).

Because information will be collected from each subjects' medical record, there is the possibility of a breach of confidentiality. However, all precautionary measures will be taken to ensure that confidentiality and privacy is maintained, and that data is stored securely. All conversations with subjects and their families will occur in a private setting.

All data will be coded. A code will be kept, but it will be kept on a password protected computer and in a password protected file separate from the data. All clinical data will be entered in RedCap, a secure web-based data management system provided by the Clinical Translational Science Institute at UCLA that only the research team will have access to. Continuous data generated from the radiological studies will be entered into a password protected Excel Sheet, on a password protected computer, that only the study team has access to. Research MRI data and analyzed information will be stored on a password protected computer with encrypted storage media.

All informed consents/assents will be stored in [name] office, which is only accessible with a key by the study team, in a locked cabinet in accordance to local IRB guidelines.

SECTION 3. METHODS

3.1 STUDY POPULATION

In this study, anticipating a 10-15% dropout rate, we plan to recruit 18 mothers: 6 healthy pregnant women, 6 women with IUGR fetuses, and 5 mothers with gestational diabetes.

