3.2.1. SCREENING

Screening will occur by a variety of methods by all primary investigators, collaborators and their colleagues. Medical charts for the potentially eligible subjects at UCLA Obstetrics and Gynecology clinics will be screened to determine eligibility by PI [name] and collaborators. A HIPAA waiver will be obtained and the information will only be collected if consent is provided. The number of subjects screened, eligible, and consented will be recorded to track recruitment.

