4.1 SAMPLE SIZES AND POWER ESTIMATES

This study will not be powered considered that this is a pilot study. Previous studies by our group in infants/children have used a sample size of 10 to 20 subjects, and these sample sizes were feasible and adequate to develop a new protocol

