4.2 AVAILABLE POPULATION

Recruitment will occur in the UCLA Santa Obstetrics and Gynecology clinic ([name]), UCLA Westwood Obstetrics and Gynecology clinic ([name]), and UCLA Maternal Fetal Medicine clinic ([name]). We anticipate based on available data, that there are approximately 10 mothers with growth restricted fetuses per month seen in the UCLA maternal fetal medicine clinic. There are approximately 12 mothers with gestational diabetes seen per month per Obstetrics and Gynecology clinic (Westwood and Santa Monica). There are approximately 40 healthy mothers seen per month per clinic.

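### Section 3.1 sets a recruitment total of 18 mothers, but the three cohorts it lists add up to 17

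*Combined protocol and SAP*

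**What the plan says.** Section 3.1 is the only place where the plan gives a sample size. After citing an anticipated dropout of 10-15%, it says "we plan to recruit 18 mothers: 6 healthy pregnant women, 6 women with IUGR fetuses, and 5 mothers with gestational diabetes". The colon makes the three cohort sizes the breakdown of the total.

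Other sections give context but no second figure:

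- Section 2.2 (Primary Outcomes), Section 3.1.1 (Inclusion and Exclusion Criteria) and Section 4.4 (Statistical Analysis Plan) refer to the same three groups: healthy, growth-restricted and gestational diabetes.
- Section 4.1 (Sample Sizes and Power Estimates) says the pilot is not powered and relies on precedent: "Previous studies by our group in infants/children have used a sample size of 10 to 20 subjects".
- Section 3.2.1 (Screening) says "The number of subjects screened, eligible, and consented will be recorded to track recruitment".
- Section 4.2 (Available Population) gives the monthly supply. For growth restriction, "there are approximately 10 mothers with growth restricted fetuses per month seen in the UCLA maternal fetal medicine clinic". For gestational diabetes, the figure is about 12 mothers per month in each of the Westwood and Santa Monica clinics.

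**The concern.** A total and its own breakdown have to agree exactly, and here they differ by one. The recruitment target is an operational number: it tells the team when each cohort is full, and it is what recruitment tracking is measured against. As written, the team cannot tell whether to stop at 17 or 18. If equal cohorts were intended, it also cannot tell whether the gestational-diabetes cohort closes at 5 or 6. That cohort is one of the three groups in the primary outcome and is the subject of the second part of Hypothesis 1.

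The stakes are modest. No power calculation depends on the figure, and the results will come from the mothers actually scanned.

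**Working it through.** **Inputs (all from Section 3.1).** Stated total 18; healthy 6; growth-restricted 6; gestational diabetes 5; dropout 10-15%.

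**Reproducing the plan's total.** 6 + 6 + 5 = 17, not 18. The gap is 18 − 17 = 1 mother, or 1/18 = 5.6%.

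**Could a fourth group supply the missing mother?** No. Sections 2.2, 3.1.1 and 4.4 name the same three groups and no other.

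**Could dropout explain the gap?** There are two possible readings.

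1. The 17 are completers and the 18 are recruits. Recruits = completers / (1 − dropout). At 10%: 17/0.90 = 18.9, rounded up to 19. At 15%: 17/0.85 = 20. Neither gives 18.
2. The 18 are recruits, and dropout is taken from them. The loss is 18 × 0.10 = 1.8 to 18 × 0.15 = 2.7 mothers, which leaves 16.2 to 15.3 completers. That is not 17.

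**Could an unstated completer target explain it?** Suppose 5 completers per cohort, 15 in all. This is an assumption; the plan states no such target.

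- Inflating each cohort: 5/0.90 = 5.6 and 5/0.85 = 5.9. Both round up to 6, giving 6 + 6 + 6 = 18.
- Inflating the total: 15/0.90 = 16.7, rounded up to 17; 15/0.85 = 17.6, rounded up to 18.

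Either total can be reached this way, so the exercise does not identify the intended one.

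**Could supply explain a smaller diabetes cohort?** Section 4.2 implies about 12 × 2 = 24 gestational-diabetes mothers per month, if the two clinics' patients do not overlap. It gives about 10 per month with growth-restricted fetuses, a cohort listed at 6. Supply therefore gives no reason for the diabetes cohort to be the smaller one. These are mothers seen, not mothers eligible or consenting, so this does not settle the intended figure either.

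**Size of the consequence.**

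| | 18 recruited | 17 recruited |
|---|---|---|
| Expected loss at 10-15% | 1.8 to 2.7 | 1.7 to 2.6 |
| Expected completers | 15.3 to 16.2 | 14.5 to 15.3 |
| Residual df, three-group ANOVA, before dropout | 18 − 3 = 15 | 17 − 3 = 14 |

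For the gestational-diabetes minus healthy comparison, assume equal SDs, no dropout, and that the diabetes cohort is the one in question. The standard error in SD units is √(1/5 + 1/6) = 0.606 with 5 against 6, and √(1/6 + 1/6) = 0.577 with 6 against 6. The ratio is 1.049, about 5% larger.

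**The case against.** The strongest reply is that this barely matters. The study is an exploratory pilot, declared unpowered, and both 17 and 18 fall within the 10 to 20 subjects cited as precedent in Section 4.1. No decision rule uses the number, and no estimate is biased by it. All of that stands, and it is why the point ranks low.

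A second reply is that nothing proves the diabetes cohort is the wrong entry. A total of 18 is also met by 7 + 6 + 5 or 6 + 7 + 5, and the plan never says the cohorts should be equal. This stands too. An equal split is the simplest reading, but it is an inference, and the standard-error comparison depends on it.

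A third reply is that the 10-15% range can generate both 17 and 18 from 15 completers. That is true, but it does not rescue the sentence: the cohorts listed as making up the 18 still add to 17, and no target of 15 is stated.

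A fourth reply is that an expected-completer count is not needed to cure an addition error. That is fair. It is a useful addition because Section 3.1 cites dropout without saying what it leaves, but the correction does not depend on it.

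**Conclusion.** The inconsistency is certain. Section 3.1 states 18 and itemises 17, within one sentence of current text, and nothing else in the document reconciles the two. Its size is one mother of 18 (5.6%), with one residual degree of freedom at stake in the ANOVA. If the diabetes cohort is the one affected and SDs are equal, the standard error of its comparison with the healthy group is about 5% larger before dropout. There is no bias and no effect on any power or significance figure. Which number was intended cannot be determined from the document; only the sponsor can say. This is a minor correction worth making because it concerns the enrolment target itself.

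**What to change.** Amend Section 3.1 so that the total and the cohorts agree: either 6 + 6 + 6 = 18, or keep 6 + 6 + 5 and restate the total as 17. Add one clause giving the expected completers at 10-15% dropout: about 15.3 to 16.2 from 18, or 14.5 to 15.3 from 17. Use the same cohort sizes as the targets when recruitment is tracked under Section 3.2.1.

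The cost is one corrected number and one clause. At most it means one gestational-diabetes mother more than the 5 listed, and none beyond the 18 already stated. Against the roughly 24 such mothers seen per month across the two clinics in Section 4.2, the effect on recruitment should be slight.

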3.1.1 INCLUSION AND EXCLUSION CRITERIA

INCLUSION CRITERIA:

- Pregnant women with singleton pregnancies (healthy cohort)
- Pregnant women with fetuses with weights < 10th percentile weight for gestational age (IUGR cohort)
- Pregnant women with gestational diabetes (diabetes cohort)

EXCLUSION CRITERIA:

- Pregnant minors
- Major congenital anomalies or disease processes in the fetus
- Fetus with known chromosomal anomalies
- Mothers who do not plan to deliver at UCLA
- Multiple pregnancy (i.e. twins, triplets, etc)
- History of claustrophobia
- Contraindications to MRI such as metallic devices in the body that are not MRI compatible

3.2.1. SCREENING

Screening will occur by a variety of methods by all primary investigators, collaborators and their colleagues. Medical charts for the potentially eligible subjects at UCLA Obstetrics and Gynecology clinics will be screened to determine eligibility by PI [name] and collaborators. A HIPAA waiver will be obtained and the information will only be collected if consent is provided. The number of subjects screened, eligible, and consented will be recorded to track recruitment.

3.2.2. CONSENT/ASSENT PROCEDURES

Consent/assent will be obtained before enrollment for all subjects and per local institutional review board guidelines. Consent will be diligently sought in an ethical manner and obtained using a multidisciplinary approach (research coordinator, principal investigators and co-investigators). Consents/assents will be provided to both English and Spanish; the process of consenting/assenting will occur in the subject's primary language. Subjects will be provided with written material, including a study flier/brochure, and will be given ample time to review the material and to ask questions. Consent will also be obtained again prior to MRI procedure.

The research team will work with the primary medical team to coordinate the introduction of the study either before or after their medical visit in order minimize disturbing the family and work-flow of the clinic.

A satisfaction survey will be obtained from participant regarding consent process, coordination of scan, MRI scan time and how we can improve our study.

SECTION 4. ANALYTICAL PLAN

4.1 SAMPLE SIZES AND POWER ESTIMATES

This study will not be powered considered that this is a pilot study. Previous studies by our group in infants/children have used a sample size of 10 to 20 subjects, and these sample sizes were feasible and adequate to develop a new protocol

4.2 AVAILABLE POPULATION

Recruitment will occur in the UCLA Santa Obstetrics and Gynecology clinic ([name]), UCLA Westwood Obstetrics and Gynecology clinic ([name]), and UCLA Maternal Fetal Medicine clinic ([name]). We anticipate based on available data, that there are approximately 10 mothers with growth restricted fetuses per month seen in the UCLA maternal fetal medicine clinic. There are approximately 12 mothers with gestational diabetes seen per month per Obstetrics and Gynecology clinic (Westwood and Santa Monica). There are approximately 40 healthy mothers seen per month per clinic.

